IB	Investigator's Brochure
IRB	Institutional Review Board
Non-UPIRTSO	Non-Unanticipated Problems Involving Risk to Subjects or Others
PHI	Protected Health Information
PI	Principal Investigator
SAE	Serious Adverse Event/Serious Adverse Experience
SOP	Standard Operating Procedure
UPIRTSO	Unanticipated Problems Involving Risk to Subjects or Others

3 Study Summary

Title	Feasibility Study of the Kronos Electrocautery Device
Protocol Name	Kronos Study
Protocol Number	SP-01, Version 1.0
Phase	N/A
Methodology	Pilot Study, Non-Randomized
Overall Study Duration (Estimated)	4 months
Subject Participation Duration (Estimated)	14 Days post procedure
Number of Sites	Up to 5
Objectives	The primary objective for this study is to assess safety and performance of the Kronos Electrocautery Device for electrocautery procedures following coaxial biopsy procedures on areas that include, but are not limited to, liver, kidney, lungs, breasts, soft tissue, etc.
Intended Purpose	The Kronos Electrocautery Device is intended to be used in electrocautery procedures to control bleeding by use of electrical current to heat the device probe tip that is applied directly to the target tissue area of treatment.
Study Design	Prospective, multicenter, single arm study with consecutive, eligible subject enrollment at each site. Patients who require a coaxial biopsy procedures on areas that include, but are not limited to, liver, kidney, lungs, breasts, soft tissue, etc., will be eligible to participate in this study.
Number of Subjects	Up to 30 patients
Primary Endpoint	Assess rate of successful electrocautery procedure in absence of procedure related Adverse Events
Inclusion Criteria	
 1. Patients undergoing a scheduled elective coaxial biopsy procedures on areas that include, but are not limited to, liver, kidney, lungs, breasts, soft tissue, etc., 2. Patients have signed an informed consent 3. Patients who are \geq 18 years of age.

Exclusion Criteria	
1. Patients with known bleeding disorder2. Significant congenital anomaly or medical problem that in the opinion of the investigator would preclude enrollment in this study.3. Women of childbearing potential who are pregnant, lactating, or planning to become pregnant during the course of the clinical investigation.4. Active systemic infection or sepsis.
Study Device	Kronos Electrosurgical Device
Duration of Use	The Kronos Electrosurgical Device is a single use probe that will be used during procedure only.
Statistical Methodology	No formal hypothesis is proposed in this protocol. All outcomes and analyses will be presented in descriptive manner only.
Applicable standards	The study will be conducted in compliance with this protocol and the following applicable regulations & Good Clinical Practices (GCPs): ISO 15444: 2020

4 Introduction

This document is a protocol for a human research study. This study will be carried out in accordance with the applicable United States government regulations, EU Regulation 2017/745 Chapter VI and Annex XV and enrolling research centers policies and procedures.

4.1 Purpose

The purpose of this feasibility study is to evaluate the safety and performance of the Kronos Electrosurgical Device to verify the in-animal models evaluated optimal withdrawal parameters in humans to reduce or prevent bleeding following a coaxial biopsy procedures on areas that include, but are not limited to, liver, kidney, lungs, breasts, soft tissue, etc.

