5.2 Potential Benefits to the Patient

Reduction or prevention of bleeding following a biopsy procedure could prevent the need of hospitalization, blood transfusion and sometimes surgery or another procedure to stop the bleeding.

6 Study Objectives

The objective of this study is to verify the in-animal models evaluated optimal withdrawal parameters in humans to reduce and control bleeding following a biopsy procedure and to assess preliminary usability evaluations of the Kronos Electrosurgical Device.

7 Study Design

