7.1 General Description

This is a multi-center, prospective, non-randomized feasibility study designed to evaluate the performance of the Kronos Electrocautery Device to verify the in-animal models evaluated optimal withdrawal parameters in humans to reduce or prevent bleeding following a biopsy procedure and to assess preliminary usability evaluations.

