10.2 Visit 2 (Treatment – Day of Biopsy procedure)

1. Ultrasound guided percutaneous biopsy will be performed as per standard of care
2. Placement of the desired core biopsy needle and guide needle will be as per standard of care
3. The needle will be removed, leaving the guide needle in place.
4. Biopsy forceps will be advanced through the guide needle to obtain the tissue
5. The biopsy forceps will be removed with the tissue
6. Remove Kronos Electrosurgery Device from packaging and visually inspect. Record Device Condition score per Attachment 1 – Kronos Scoring Criteria
7. Using the current Instruction for Use (IFU), the Kronos Electrosurgery Device will be advanced to a predetermined length (recorded) to ensure that it protrudes into the biopsy track. Record Maneuverability to Target Tissue score per Attachment 1 – Kronos Scoring Criteria. If Guide needle was used, record Compatibility with guide needle score per Attachment 1 – Kronos Scoring Criteria
8. The Kronos Electrosurgery Device will be activated, and the device and guide needle will

be withdrawn simultaneously at controlled speed. The total time of withdrawal (recorded). Record Withdrawal Force score per Attachment 1 – Kronos Scoring Criteria

9. Any blood or fluids from the access site will be soaked up with a dry gauze without placing any pressure on the access site.
10. Blood or other fluids will be collected for a minimum of five minutes, or until all bleeding has stopped (if applicable). The gauze will be weighed (recorded) to estimate the blood loss with results. Record Device Performance (Blood control) score per Attachment 1 – Kronos Scoring Criteria.
11. This procedure will be performed a single time, on areas that include, but are not limited to, liver, kidney, lungs, breasts, soft tissue, etc.,.. The biopsy procedure is being performed as a standard of care, which may require multiple passes.

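### Does the aim of verifying animal-derived withdrawal parameters need a stated criterion and a named analysis?

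*Combined protocol and SAP*

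**What the plan says.** Three sections state the aim in nearly the same words. Section 4.1 (Purpose) has "to verify the in-animal models evaluated optimal withdrawal parameters in humans to reduce or prevent bleeding following a coaxial biopsy procedures", after the evaluation of safety and performance. Section 6 (Study Objectives) puts it first: "The objective of this study is to verify the in-animal models evaluated optimal withdrawal parameters in humans to reduce and control bleeding", with preliminary usability as the other objective. Section 7.1 (General Description) again says "verify the in-animal models evaluated optimal withdrawal parameters in humans to reduce or prevent bleeding following a biopsy procedure", after the evaluation of performance.

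The technique is in Section 10.2. Step 7 opens with "Using the current Instruction for Use (IFU") and says the device "will be advanced to a predetermined length (recorded"), "to ensure that it protrudes into the biopsy track". In step 8 the activated device and the guide needle are to "be withdrawn simultaneously at controlled speed", followed by "The total time of withdrawal (recorded"). Gauze weight and a blood-control score are recorded afterwards.

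The Study Summary (Section 3) names safety and performance as the primary objective. Its primary endpoint is the rate of successful procedures free of procedure-related adverse events. The outcome lists that follow Section 7.3 cover hematoma, blood loss, need for ultrasound, reintervention and time to discharge. Section 3 also says that there is no formal hypothesis and that all results are descriptive. Section 11.1 calls the sample size of 30 non-statistical, and Section 8.3 gives an accrual target of at least 20.

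**The concern.** To verify something normally takes three things: a value to check, a tolerance around it, and a result that settles the matter. The supplied text has none of them. The length is predetermined and the speed is controlled, but neither has a number, and the instructions for use are cited without a version. The one animal study in the reference list, in porcine liver, is not visibly cited in the body of the text, so the source of the parameters is unclear too.

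The two quantities closest to the aim, length and withdrawal time, are then named in no endpoint, outcome or analysis. The Withdrawal Force score in Attachment A sounds relevant, but it grades friction on removal rather than speed or time.

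Two things would be at stake. An objective stated three times could be reported neither as met nor as not met. And, with no criterion fixed in advance, a claim of verification could be attached after the fact to almost any set of results.

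**Working it through.** The plan has no figure to reproduce on this point. It gives no alpha, power, margin or target rate, and it says the 30 patients were not statistically derived. The check is therefore mainly a comparison of sections, followed by a look at what a criterion could deliver.

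**1. What each element of the aim has in the text**

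| Element | Where it would appear | What is there |
|---|---|---|
| Parameter values | Sections 4.1, 6, 7.1, 10.2 | None; the instructions for use are cited for device use |
| Tolerance | Section 10.2 | None |
| Criterion for verification | Sections 6, 11 | None |
| Length and withdrawal time | Section 10.2 | Recorded for each patient |
| Withdrawal distance | Section 10.2 | Not listed, so speed may not be derivable |
| Bleeding result | Section 10.2, primary outcomes | Gauze weight, blood-control score, hematoma, need for ultrasound |
| Analysis | Sections 3, 11 | Descriptive for all outcomes; length and time not named |

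The gap is real for values, tolerance and criterion. Two limits apply. The instructions for use and the Investigator's Brochure are not among the documents, so values may exist there. And the primary endpoint does not define a successful procedure, so the text does not settle whether success includes withdrawal as specified.

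**2. Does any stated rule give a wrong result?** No. The endpoint, the outcomes, the missing-data rule and the descriptive presentation all work without the criterion. Every patient is treated under one technique and bleeding is then measured. For a feasibility study, seeing how bleeding behaves in humans under the technique carried over from animals is a natural reading of the aim.

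**3. What would a criterion add?** Suppose one existed and x of n patients met it. The exact (Clopper-Pearson) 95% limits are the 2.5% quantile of Beta(x, n − x + 1) and the 97.5% quantile of Beta(x + 1, n − x). When x = n, the lower limit is 0.025^(1/n) and the upper limit is 100%.

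- n = 30, x = 30: 0.025^(1/30) = 0.884, so 88.4% to 100%.
- n = 30, x = 27 (assumed): 73.5% to 97.9%, a width of 24.4 points.
- n = 20, x = 20: 0.025^(1/20) = 0.832, so 83.2% to 100%.
- n = 20, x = 18 (assumed): 68.3% to 98.8%, a width of 30.5 points.

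These intervals describe one arm. The protocol sets no comparator and no performance goal, and it leaves the mix of organs open. No count in this range could show that the parameters reduce bleeding.

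**4. What would linking withdrawal time to bleeding add?** For an observed correlation of 0, the 95% limits on the Fisher z scale are ±tanh(1.96/√(n − 3)).

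- n = 30: tanh(1.96/√27) = tanh(0.377) = 0.36.
- n = 20: tanh(1.96/√17) = tanh(0.475) = 0.44.

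A correlation anywhere from about −0.36 to 0.36 would remain possible with 30 patients. The direction of bias is also awkward. If speed is held steady, total time varies mainly with the depth of the track, and depth plausibly varies with the organ. A plot of bleeding against time would then largely show depth and organ.

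**The case for a change.** The strongest case for a change is that it asks for no test, no power calculation and no extra patients. Verification is the protocol's own word, and Section 6 puts it first. A descriptive study should still say which result answers its objective, and instructions for use do not supply a study criterion. Citing a source and stating a descriptive criterion before enrolment would be cheap, because Section 13.3 says the case report forms are still to be developed. It would also close the door on a claim made after seeing the data.

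Much of this stands. On the supplied text, the aim cannot be declared met by any rule, and a report that announced the parameters as verified would go beyond the plan.

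It does not carry the point to a required change. The values and the criterion could come only from the sponsor, and a pass level would come close to a performance goal in a study designed to be descriptive. The guard against overclaiming is already there: with one arm, no hypothesis and descriptive presentation only, the plan supports no conclusion that bleeding was reduced. Nor can it be said that everything needed is already collected, since withdrawal distance is not listed. If speed is the parameter of interest, a criterion alone would not make it assessable.

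**Conclusion.** The observation is accurate, but it describes missing detail that an analyst can handle sensibly. The recorded length, withdrawal time, blood loss, blood-control score and hematoma can be summarised under the descriptive plan, and the result presented as bleeding observed in humans under the technique in the instructions for use. Speed can be reported only if distance turns out to have been recorded.

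No endpoint, estimate or patient number changes. The cost of leaving the text alone is one loosely worded aim. The gain from a criterion would be a single proportion with a lower 95% limit of at best 88.4% at 30 patients or 83.2% at 20, without a comparator.

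This rests on three assumptions: the study stays descriptive; the safety, performance and usability aims remain the main product; and the report does not present verification as a formal finding. If the sponsor meant to rely on these data to claim that the parameters had been verified or that bleeding had been reduced, the conclusion would be different.

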4.2 Background

Ultrasound-guided percutaneous liver and kidney biopsies are used widely for the diagnosis, staging and follow-up of hepatic and renal disease. Complications of these procedures include pain, bleeding, pneumothorax, bile peritonitis, arteriovenous fistula formation, glomeruli in kidney biopsies, hemorrhage, and others. Of the serious complications, bleeding is the most common, with an incidence ranging from 0.8 percent (%) to 1%, and subsequent fatality may occur in as many as three (3) out of 10,000 liver biopsies. Similarly, the bleeding complications from kidney biopsies have been reported as between 9% to 34%.^{1,2,3} In addition, bleeding from breast biopsies have occurred in incidences ranging from 6.6% to 8.2%, and occurrences of bleeding from lung biopsies range from .6% - 17.6%.⁵

5 Risk Benefit Analysis

5.1 Risks to the Patient -FMEA

No additional risks are associated with the use of Kronos Electrosurgical Device compared to existing electrocautery devices.

POTENTIAL ADVERSE EVENTS

Possible complications associated with the use of the Kronos device are similar to those associated with electrocautery devices and include, but may not be limited to:

Common (occurs in more than 10% of patients undergoing this type of procedure):

- Pain – study device or standard of care biopsy related
- Hemorrhage/Bleeding – study device or standard of care biopsy related
- Internal and external burn – study device related
- Scarring – study device or standard of care biopsy related

Less Common (occurs in 1-10% of patients undergoing this procedure):

- Reintervention - – study device or standard of care biopsy related

Rare (occurs in less than 1% of patients undergoing this type of procedure):

- Allergic Reaction – study device or standard of care biopsy related
- Inflammatory Response - – study device or standard of care biopsy related
- Infection - study device or standard of care biopsy related
- Death - study device or standard of care biopsy related
- Interference with implantable device – study device related

5.2 Potential Benefits to the Patient

Reduction or prevention of bleeding following a biopsy procedure could prevent the need of hospitalization, blood transfusion and sometimes surgery or another procedure to stop the bleeding.

6 Study Objectives

The objective of this study is to verify the in-animal models evaluated optimal withdrawal parameters in humans to reduce and control bleeding following a biopsy procedure and to assess preliminary usability evaluations of the Kronos Electrosurgical Device.

7 Study Design

7.1 General Description

This is a multi-center, prospective, non-randomized feasibility study designed to evaluate the performance of the Kronos Electrocautery Device to verify the in-animal models evaluated optimal withdrawal parameters in humans to reduce or prevent bleeding following a biopsy procedure and to assess preliminary usability evaluations.

7.2 Number of Subjects

Up to 30 subjects

7.3 Duration of Participation

Up to 14 days

7.4 Primary Study Outcomes

Absence of Hematoma formation

Measure and categorize amount of blood loss from biopsy access site

Absence of the need for ultrasound examination due to observation of bleeding

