7.4 Secondary Study Outcomes

Absence of secondary reintervention

Time to hospital discharge

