8.1 Inclusion Criteria

1. Patients undergoing a scheduled elective coaxial biopsy procedures on areas that include, but are not limited to, liver, kidney, lungs, breasts, soft tissue, etc.,
2. Patients have signed an informed consent
3. Patients who are ≥ 18 years of age.

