9.1 Description

The Kronos Electrocautery Device (**Figure 1**) is a disposable electrocautery device that can cauterize deep tissue through a standard biopsy procedure guide needle. This device is intended to coagulate the tissue surrounding the core biopsy channel during withdrawal to reduce or eliminate significant post-procedural bleeding. Currently, the Kronos Electrocautery Device consists of one (1) size. As such, the existing Kronos Electrocautery Device is chosen as the worst-case condition.

Figure 1: Kronos Electrosurgery Device

10 Study Procedures

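### The third primary outcome names only ultrasound and leaves its trigger undefined, so bleeding investigated by another imaging method does not count against it

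*Combined protocol and SAP*

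**What the plan says.** Section 7.4 (Primary Study Outcomes) lists three items without further definition:

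- The first is "Absence of Hematoma formation".
- The second is external bleeding: blood lost at the access site is to be measured and put into categories.
- The third, which is at issue here, is "Absence of the need for ultrasound examination due to observation of bleeding".

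The Study Summary (Section 3) gives a differently worded primary endpoint: "Assess rate of successful electrocautery procedure in absence of procedure related Adverse Events". The secondary outcomes include "Absence of secondary reintervention".

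Eligibility is open-ended. Section 8.1 admits "Patients undergoing a scheduled elective coaxial biopsy procedures on areas that include, but are not limited to, liver, kidney, lungs, breasts, soft tissue, etc", and step 11 of Section 10.2 repeats that organ list. Step 1 of Section 10.2, however, describes one form of guidance only: "Ultrasound guided percutaneous biopsy will be performed as per standard of care".

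Section 9.1 describes the device as "intended to coagulate the tissue surrounding the core biopsy channel during withdrawal to reduce or eliminate significant post-procedural bleeding". The only bleeding measurement scheduled in Section 10.2 (steps 9 and 10) is the weight of gauze used at the access site. Neither Section 10.2 nor the schedule in Section 10.3 contains an imaging step after the device is withdrawn.

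**The concern.** The item is meant to show how often bleeding after the procedure led to an imaging examination. It is tied to one method, while the trial accepts organs for which bleeding might be investigated in another way. It also depends on an observation that the protocol does not describe. The device acts along the deep biopsy channel, where bleeding may not show at the skin, so the meaning of that word matters.

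Three things are at stake:

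- A literal reading can remove failures from this item but cannot add any, so any error from the choice of method favours the device.
- Up to five sites may score the same case differently.
- The item may not mean the same thing in a liver patient as in a lung patient, although nothing in the plan calls for it to be shown by organ.

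**Working it through.** The plan gives no figure to reproduce. Section 11.1 states that the 30 patients are not statistically derived, and the Study Summary limits the analysis to description. The check is therefore a reading of the text, followed by the effect of one patient.

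**1. How the item scores four cases, read literally**

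| Case | Third primary outcome |
|---|---|
| Ultrasound because bleeding was seen | Fails |
| CT or X-ray because bleeding was seen | Does not fail: no ultrasound was needed |
| Ultrasound because internal bleeding was suspected (for example from pain or a fall in blood pressure) | Either way: the trigger is undefined |
| CT or X-ray because internal bleeding was suspected | Does not fail |

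No other section extends the item to other methods. None says who decides or over what period. The period cannot be inferred either: Section 7.3 gives participation of up to 14 days, and Section 12.1.4 gives a follow-up period of up to 30 days.

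**2. Whether other outcomes catch these cases**

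- *Hematoma (7.4):* not tied to a method, so it can catch an internal bleed. But it has no detection method, size or time window, and no imaging is scheduled.
- *Blood loss (7.4):* external only, at the access site.
- *Adverse-event-free success (Study Summary):* can catch a bleed that is recorded and judged procedure related. Bleeding is a listed event (5.1), hemorrhage is classed as serious (12.1.3), and Section 12.2 requires all adverse events to be recorded. An examination that was done for bleeding and found nothing further need not appear here.
- *Reintervention (secondary):* catches only bleeding that led to a further intervention.

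The cover is real but partial.

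**3. Effect of one patient**

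Inputs: n = 30 (Section 11.1) and n = 20 (minimum accrual, Section 8.3). One patient moved from success to failure changes the rate by 1/n:

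- n = 30: 1/30 = 3.3 percentage points
- n = 20: 1/20 = 5.0 percentage points

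For scale, exact (Clopper-Pearson) 95% intervals, which the plan does not itself prescribe:

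| n | No patient reclassified | One patient reclassified |
|---|---|---|
| 30 | 30/30 = 100% (88.4 to 100) | 29/30 = 96.7% (82.8 to 99.9) |
| 20 | 20/20 = 100% (83.2 to 100) | 19/20 = 95.0% (75.1 to 99.9) |

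**4. Why the number of patients affected is left open**

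It would need the organ mix, the bleeding rate and the share of bleeds investigated without ultrasound. Only bleeding rates are given (Section 4.2; for lung, 0.6% to 17.6%). If 10 of 30 patients had lung biopsies, which is an assumption, the expected number of bleeds would be 10 × 0.006 = 0.06 to 10 × 0.176 = 1.76. These are bleeds, not examinations, so even this range does not give the number misclassified.

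**The case against.** The strongest case against has four parts.

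*No scoring rule exists.* A reader might infer that the protocol scores a patient imaged by another method as a success. It does not say so. Section 7.4 is a bare list, and the effect is confined to this one item. The same patient can still fail on hematoma, on the adverse-event-free endpoint or on reintervention. This stands as a limit on the claim, but the cover has the gaps shown above, and a listed primary outcome should carry its own meaning.

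*Observation need not mean visible blood.* A reader might infer that ultrasound for suspected internal bleeding is always counted as success. The text does not support that: external loss is a separate item, and bleeding detected clinically could be called observed. This stands. What remains is that the wording permits both scorings.

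*Step 1 of Section 10.2 prescribes ultrasound guidance.* This has less force. Guidance during the biopsy does not settle how later bleeding is investigated, and step 11 repeats the open organ list. It is true, though, that no section says CT or X-ray would be used. That such cases will occur is an assumption.

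*The study is a descriptive pilot.* No hypothesis or success threshold depends on the item. That limits the consequence but does not remove it, because the rate will still be reported as a primary result.

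**Conclusion.** The point holds in a limited form. The third primary outcome is specific to one method and has an undefined trigger, in a trial open to any organ. Read literally, bleeding investigated by another method does not count against the item, which biases that item towards success. Ultrasound for suspected internal bleeding may be scored differently from site to site.

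The size is 3.3 points per affected patient at n = 30 and 5 points at n = 20. How many patients are affected is unknown and may be none. A reader might infer a substantial overstatement of device success overall. The documents do not support that, because they give no organ mix and no rate of imaging by method, and other outcomes can register the same bleeds.

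The conclusion rests on a literal reading of Section 7.4 and on the possibility, which the documents neither state nor exclude, that bleeding in some eligible organs is investigated without ultrasound. The wording should be changed before data are summarised, and preferably before enrolment.

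**What to change.** Reword the third item in Section 7.4 as: *absence of any unplanned imaging (any modality) after device withdrawal prompted by observed or suspected bleeding*. State the follow-up window, which is for the sponsor to set, and name the role that judges whether an examination qualifies.

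Record the method and the trigger of each such examination on the CRF. Report the item overall and by method and organ.

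Separately, reconcile step 1 of Section 10.2, which describes ultrasound-guided biopsy only, with the open organ list in Section 8.1 and in step 11 of Section 10.2.

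The cost is a short change to Section 7.4, fields for method and trigger on CRFs that Section 13.3 says are still to be developed, and a small descriptive table. No additional imaging is requested. There are two downsides: the success rate may be slightly less favourable, and suspected bleeding involves some judgement, which recording the trigger makes visible.
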